4.4.3 Deaths

All deaths recorded on the TERM page, the AE page, or SAE page (with a death date, cause of death, outcome or SAE categorization present) of the CRF will be considered a death in the analyses. All deaths will be summarized by SOC and PT for the safety analysis. A listing of all deaths during screening and double-blind treatment period will be produced.

4.4.4 Serious adverse events

The subject incidence of treatment emergent SAEs will be presented by SOC, PT and treatment group. In addition, the subject incidence of related treatment emergent SAEs will be presented by SOC, PT, and treatment group for the safety analysis. A listing of all SAEs during screening and double-blind treatment period will be produced. If we cannot determine whether an AE is serious, it will be considered an SAE.

4.4.5 Related adverse events

The subject incidence of related treatment emergent AEs will be presented by SOC, PT and treatment group for safety analysis.

The subject incidence of most common related treatment emergent AEs (reported in at least 2% of the subjects in any treatment group) during the double-blind treatment period will be presented by PT and treatment group for safety analysis.

4.4.6 Adverse events leading to discontinuation

Number of subjects who discontinue during the screening phase due to an AE will be listed.

Treatment emergent AEs leading to study treatment discontinuation will be summarized by SOC, PT, and treatment group for safety analysis.

In addition, a subject listing of discontinuations due to AEs will be presented for screening and double-blind treatment period.

4.4.7 Other adverse events analyses

Treatment emergent AEs in subjects with any of the following at any time during the treatment phase will be listed:

- CK > 10x upper limit or normal (ULN)
- Alanine aminotransferase (ALT) or Aspartate aminotransferase (AST) ≥ 3 x ULN and TBL ≥ 2 x ULN on one occasion
- Serum creatinine increase > 100% from baseline and > ULN
- Shift in urine protein from none/trace at baseline to ++ or greater
- Shift in urine blood from none/trace at baseline to ++ or greater
- Subjects with proteinuria, hematuria or both at any time

4.5 Clinical laboratory tests evaluation

All scheduled laboratory evaluations are performed by central laboratories. Evaluations done by local laboratories, if any, will not be included in summary tables nor in the listings. All safety measurements will use all available data for analyses, including data from unscheduled visits and repeated measurements. For lab assessment summary by visit, the data will be summarized according to the protocol-scheduled week for that visit. For lab

summaries that are not visit-based, all visits including unscheduled and repeat visits will be included.

Laboratory parameters will be presented both in SI and conventional units where appropriate.

If a laboratory test is reported as above or below the limit of quantification (i.e., result includes operator $>$, \geq , $<$, or \leq), the limit of quantification will be used for analysis. The result with the operator will be reported in listings.

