#### Hy's Law (HL)

AST or ALT  $\geq 3x$  ULN **together with** TBL  $\geq 2x$ ULN, where no other reason, other than the IMP, can be found to explain the combination of increases, eg, elevated ALP indicating cholestasis, viral hepatitis, another drug.

For PHL and HL the elevation in transaminases must precede or be coincident with (i.e. on the same day) the elevation in TBL, but there is no specified timeframe within which the elevations in transaminases and TBL must occur.

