### 12.3.3 Identification of potential hy's law cases

In order to identify cases of PHL it is important to perform a comprehensive review of laboratory data for any patient who meets any of the following identification criteria in isolation or in combination:

- ALT  $\geq 3x$ ULN
- AST  $\geq 3x$ ULN

- $TBL \geq 2xULN$

When a patient meets any of the identification criteria, in isolation or in combination, the central laboratory will immediately send an alert to the Investigator (also sent to AstraZeneca representative).

The Investigator will also remain vigilant for any local laboratory reports where the identification criteria are met, where this is the case the Investigator will:

- Notify the AstraZeneca representative
- Request a repeat of the test (new blood draw) by the central laboratory
- Complete the appropriate unscheduled laboratory CRF module(s) with the original local laboratory test result

When the identification criteria are met from central or local laboratory results the Investigator will without delay:

- Determine whether the patient meets PHL criteria (see Section 12.3.2 of this Appendix for definition) by reviewing laboratory reports from all previous visits (including both central and local laboratory results)

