4.5.2 Shift tables and summary of subjects with specific laboratory values

The hematology and chemistry data will also be summarized in shift tables comparing results of extreme values over the duration of the double-blind treatment period against the baseline, based on normal range categories.

Urine blood and urine protein will be summarised by

- (1) category of most abnormal result and
- (2) by category at the final visit, relative to baseline categories (shift tables) for each treatment group.

Numbers and percent of subjects who developed proteinuria (defined as an increase in the dipstick urine protein measurement of at least ++ from baseline to any visit after baseline (e.g. negative/trace to ++, + to +++, ++ to +++++)) will be presented by treatment group. Similar summaries will be made of hematuria (defined as an increase in the dipstick urine blood measurement of at least ++ from baseline to any visit after baseline (e.g. negative/trace to ++, + to +++, ++ to +++++)) and concurrent proteinuria and hematuria.

Similar tables will summarise shift in urine protein/blood categories from none or trace at baseline to the categories of urine protein/blood at the last visit.

Elevations of ALT [≥ 3 times the ULN on single occasions and two consecutive occasions (defined as any 2 assessments taken on, at either a scheduled or unscheduled visit)] and CK (≥ 5 times and ≥ 10 times the ULN) and percentage increases from baseline in creatinine (including $>30\%$ and $\leq 50\%$; $>50\%$ and $\leq 100\%$; and $> 100\%$, split by \leq ULN and $>$ ULN) at any time point during the treatment phase will be highlighted and summarised by treatment group at time of occurrence.

Elevated ALT and/or AST and Total Bilirubin

The following criteria will be summarized in examination of elevated ALT and/or AST and total bilirubin (TBL):

AST or ALT $\geq 3 \times$ ULN together with TBL $\geq 2 \times$ ULN at any point during the study following the start of study medication irrespective of an increase in ALP.

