4.6.4 Post-dosing Safety Observations

The following conventions are for the safety analysis during the 104-week randomized double-blind treatment period.

Randomized treatment period safety observations will be listed regardless of whether the subject was taking blinded study drug. However, safety observations will not contribute to summaries if the subject's last dose of blinded drug was as follows:

- All AEs, including SAEs, will be summarized only if their onset dates were within 10 days after last dose of study drug.
- Vital signs, physical examination, safety laboratory and ECG results will be summarized only if measured on or before the 14th day after the last blinded drug dosing date.

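### SAP 4.5 excludes local-laboratory results from tables and listings, although Protocol Appendix C uses them to identify potential Hy's Law cases, so a case seen only locally is absent from every laboratory output

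*SAP*

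**What the plan says.** **Protocol.** Appendix C (12.3.2) defines PHL as ALT or AST at or above 3 x ULN together with total bilirubin at or above 2 x ULN, at any time in the study after treatment starts. The transaminase rise must come first or fall on the same day, but "there is no specified timeframe within which the elevations in transaminases and TBL must occur". Under 12.3.3 the investigator decides whether a patient qualifies "by reviewing laboratory reports from all previous visits (including both central and local laboratory results"). When a local result triggers the check, the site requests a central repeat on a new draw and records the original local value on the unscheduled laboratory CRF module.

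**SAP.** Four rules bear on how such cases are reported:

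- Section 4.5, on local results: "Evaluations done by local laboratories, if any, will not be included in summary tables nor in the listings". The next sentence reads: "All safety measurements will use all available data for analyses, including data from unscheduled visits and repeated measurements".
- Section 4.5.2 summarizes the combined liver criterion "at any point during the study following the start of study medication irrespective of an increase in ALP". This is essentially the Appendix C wording, without the rule on order and interval.
- Section 4.4.7 lists treatment-emergent AEs in subjects selected on laboratory criteria. One is a transaminase elevation with "TBL ≥ 2 x ULN on one occasion".
- Section 4.6.4 says that safety laboratory results, among others, "will be summarized only if measured on or before the 14th day after the last blinded drug dosing date". The same section says that treatment-period safety observations are listed whether or not the subject was on drug.

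**The concern.** The protocol collects local liver values because they may signal drug-induced liver injury, and it lets them decide whether a case exists. The SAP then removes those values from the tables and also from the listings, where a reader would otherwise look for them. The reported number of PHL subjects can therefore be lower than the number found under the protocol's own definition. A Hy's Law SAE could even be on file while the laboratory table shows no qualifying subject.

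The other two rules are a smaller matter. They leave the SAP with more than one operational definition of the same event, so two programmers could produce different PHL counts from the same data.

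**Working it through.** The plan gives no figure to reproduce. The check traces four types of case through each rule.

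| Case | Appendix C | SAP 4.5.2 summary | SAP 4.4.7 AE listing | Laboratory listings |
|---|---|---|---|---|
| A. Both thresholds crossed at a local laboratory only; central repeat below them | PHL | Out (4.5) | Not selected, if selection uses the 4.5 data | Out (4.5) |
| B. Central ALT/AST over threshold at one visit, central bilirubin over threshold at a later visit, both on treatment | PHL | In, if programmed with the Appendix C timing rule; the SAP wording does not settle it | Out, if one occasion means one assessment | In |
| C. Central ALT/AST over threshold on treatment, central bilirubin over threshold on day 16 after last dose | PHL, if the sample still counts as within the study | Out, since 16 > 14 | Out on the same reading as B | In (4.6.4) |
| D. Both thresholds crossed in one central sample on treatment | PHL | In | In, if the subject has a treatment-emergent AE | In |

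Only case A is lost from all laboratory outputs. Whether it appears elsewhere depends on AE reporting:

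1. Protocol 6.3.7 says that the combined elevation is to be reported as an SAE. Read literally, that brings case A into the SAE tables.
2. Appendix C is narrower. It calls for an SAE if the case meets serious criteria, if no explanation other than the study drug is agreed, or if the assessment is delayed beyond 3 weeks. Under 12.3.5, if the agreed explanation is not itself an AE, it is only recorded on the CRF.
3. Protocol 6.3.6 otherwise limits AEs based on protocol-mandated laboratory tests to those that meet an SAE criterion or cause treatment to be stopped.
4. AE collection (Protocol 6.3.1) and AE summaries (SAP 4.6.4) both end 10 days after the last dose.

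A local-only PHL case with an agreed non-AE explanation, handled under Appendix C, therefore need have no record in any table or listing of laboratory data or AEs.

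**Sampling interval.** After week 13, scheduled chemistry falls at weeks 39, 65, 91 and 104. The gaps are 39 − 13 = 26, 65 − 39 = 26, 91 − 65 = 26 and 104 − 91 = 13 weeks. A peak between visits would be caught only on an unscheduled sample. This shows why unscheduled samples matter; it does not show how many were analysed locally.

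**The case against.** The case for leaving the SAP alone has real substance.

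- **Central-only tables are a common choice.** They avoid mixing assays and reference ranges. Protocol 8.5.3 promises only descriptive summaries, and Appendix C sets out how to identify and report cases, not how to tabulate them. This stands for by-visit summaries. It does not explain removing local values from listings, or a PHL count that ignores values which define PHL.
- **Other routes catch many cases.** A hospital admission for the event is an SAE, a laboratory change that leads to stopping drug is an AE, and a local alert triggers a central repeat. All of this is true. But a later draw can miss a transient peak, and the AE route has the gap shown in the working.
- **The one-occasion condition is not in the PHL table.** A reader might infer that the SAP requires simultaneous elevations throughout. It does not: the condition is confined to the 4.4.7 AE listing and might even mean at least one occasion. What remains is an ambiguity that the SAP should settle.
- **Day 14 removes nothing from listings.** A reader might infer that late values disappear altogether, but SAP 4.6.4 cuts summaries only. The early termination visit is planned within 1 week of stopping (Protocol 4.2.11), so scheduled samples normally fall inside the window. The remaining exposure is a late unscheduled value missing from the PHL summary.
- **Creatine kinase.** A reader might extend the point to locally measured CK peaks. Appendix D asks for prompt measurement after muscle symptoms but names no local laboratory, and Protocol 5.2.1 makes central analysis the default. Nothing says that local CK is captured, and myopathy must be recorded as an AE. The documents do not support a CK finding.

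The SAP's table of changes from the protocol (section 6) is redacted, so a declared departure cannot be ruled out.

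**Conclusion.** The conflict between SAP 4.5 and Protocol Appendix C is real and can undercount protocol-defined PHL cases in the laboratory outputs. The timing condition in SAP 4.4.7 and the day-14 cut in 4.6.4 are lesser inconsistencies in how the same event is defined. It would go too far to say that such cases vanish from the safety report: many would surface as AEs or SAEs, and late central values remain listed.

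The size cannot be estimated, because the documents give neither the rate of PHL nor the share of samples analysed locally. The practical scale is one or very few subjects, but for an event this rare one subject is the difference between a reported count of 1 and 0. The conclusion assumes that sites enter local values as 12.3.3 instructs and that SAP 4.5 is programmed as written. The point merits a change to the SAP; it does not bear on the efficacy analysis.

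**What to change.** 1. **SAP 4.5.** List all local liver results recorded in the CRF, flagged as local and expressed as multiples of the local ULN. Derive the PHL summary from central plus local results and keep by-visit summaries central-only. State how this fits with the sentence on using all available data.
2. **SAP 4.4.7 and 4.5.2.** Use the single Appendix C definition in both places: transaminase rise before or on the same day as the bilirubin rise, with no limit on the interval between them.
3. **SAP 4.6.4.** Exempt the PHL summary from the 14-day cut.
4. **CK.** Apply the same listing rule to local CK values only if they are captured in the CRF.
5. **Protocol 6.3.7 and Appendix C 12.3.5.** These differ on when a combined elevation becomes an SAE and must be reconciled, because the SAE tables are the main fallback for cases missing from the laboratory outputs.

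The cost is SAP wording and some added programming. Appendix C already has the local liver values entered in the CRF. Local reference ranges are also needed; the documents do not say whether they are collected, so this should be confirmed first.

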4.5.1 Summary of laboratory variables over time

Descriptive statistics (number of observations, mean, SD, minimum, median and maximum values) for collected values, change from baseline, and percentage change from baseline will be summarized for clinical laboratory tests (hematology, chemistry, urinalysis, lipid profile) at each protocol scheduled nominal visit and at the last non-missing post-baseline visit, across treatment groups.

Hepatic biochemistry and CK values as well as their changes from baseline, plus change from baseline and percentage change from baseline in creatinine, will be summarised using descriptive statistics at each visit.

Hematology, hepatic biochemistry (including CK) and clinical chemistry values outside the laboratory reference ranges will be flagged and summarised.

Urinalysis data including pH and specific gravity will be summarised by mean, median, SD, minimum, maximum, and number of subjects for each treatment group at each visit.

4.5.2 Shift tables and summary of subjects with specific laboratory values

The hematology and chemistry data will also be summarized in shift tables comparing results of extreme values over the duration of the double-blind treatment period against the baseline, based on normal range categories.

Urine blood and urine protein will be summarised by

- (1) category of most abnormal result and
- (2) by category at the final visit, relative to baseline categories (shift tables) for each treatment group.

Numbers and percent of subjects who developed proteinuria (defined as an increase in the dipstick urine protein measurement of at least ++ from baseline to any visit after baseline (e.g. negative/trace to ++, + to +++, ++ to +++++)) will be presented by treatment group. Similar summaries will be made of hematuria (defined as an increase in the dipstick urine blood measurement of at least ++ from baseline to any visit after baseline (e.g. negative/trace to ++, + to +++, ++ to +++++)) and concurrent proteinuria and hematuria.

Similar tables will summarise shift in urine protein/blood categories from none or trace at baseline to the categories of urine protein/blood at the last visit.

Elevations of ALT [≥ 3 times the ULN on single occasions and two consecutive occasions (defined as any 2 assessments taken on, at either a scheduled or unscheduled visit)] and CK (≥ 5 times and ≥ 10 times the ULN) and percentage increases from baseline in creatinine (including $>30\%$ and $\leq 50\%$; $>50\%$ and $\leq 100\%$; and $> 100\%$, split by \leq ULN and $>$ ULN) at any time point during the treatment phase will be highlighted and summarised by treatment group at time of occurrence.

Elevated ALT and/or AST and Total Bilirubin

The following criteria will be summarized in examination of elevated ALT and/or AST and total bilirubin (TBL):

AST or ALT $\geq 3 \times$ ULN together with TBL $\geq 2 \times$ ULN at any point during the study following the start of study medication irrespective of an increase in ALP.

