### **3.9 Discontinuation of investigational product**

Subjects may be discontinued from investigational product in the following situations, at the discretion of the investigator(s):

- Subject decision. The subject is at any time free to discontinue treatment, without prejudice to further treatment.
- An AE that in the opinion of the investigator warrants subject withdrawal.
- Severe non-compliance with the study protocol.
- Withdrawal of informed consent.
- CK >10 x ULN accompanied by muscle pain, tenderness, or weakness; see Appendix D for management of increased creatine kinase.
- ALT or AST >3 x ULN; see Appendix C for further instruction on cases of increases in liver biochemistry and evaluation of Hy's Law.
- Deterioration in the subject's condition that in the opinion of the investigator warrants subject withdrawal.
- At investigator's discretion.
- Development of a condition that made the subject high-risk, such as clinical atherosclerotic disease (MI, transient ischemic attack, stroke, angina pectoris, symptomatic CAD, peripheral arterial disease, abdominal aortic aneurysm) or diabetes mellitus.

Subjects will be monitored to ensure that they are within the entry criteria limits for LDL-C throughout the study. Subjects will be discontinued from the treatment in 1 of 2 circumstances based on a subject's inclusion criteria:

1. Subjects with no additional CVD risk factors other than age and hypertension, and subjects without hypertension who have 3 or more other risk factors (including age) will be discontinued from the treatment if their LDL-C levels are  $\geq 160$  mg/dL (4.1 mmol/L) on 2 consecutive visits during the study.
2. Subjects without hypertension who have fewer than 3 other risk factors (including age) will be discontinued from the treatment if their LDL-C levels are  $\geq 190$  mg/dL (4.9 mmol/L) on 2 consecutive visits during the study.

The results of the LDL-C determinations will remain unblinded to the central laboratory but will be blinded to the investigator and site personnel after screening. A flag on the central laboratory report will notify the investigator that the subject should be removed from the study. The subject will be discontinued from the study and complete the Early Termination visit procedures. Subsequent treatment will be advised by the investigator based on local guidelines.

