**Table 2 Laboratory Safety Assessments**

Hematology (whole blood)	Clinical Chemistry (serum or plasma)	Urinalysis
Hemoglobin	Alanine aminotransferase	Color
Erythrocytes	Aspartate aminotransferase	Appearance
Hematocrit	Creatine kinase	Specific gravity
Leukocyte cell count	Gamma-glutamyltransferase	Urine reaction pH
Platelet count	Alkaline phosphatase	Glucose
Red cell distribution width	Total bilirubin	Protein (qualitative)
Mean corpuscular volume	Sodium	Ketones
Mean corpuscular hemoglobin	Potassium	Bilirubin
Mean corpuscular hemoglobin concentration	Calcium	Occult blood
Percentage differential leukocyte count	Total protein	Microscopic analysis of any formed elements
	Phosphate	
	Albumin	
	Creatinine	
	Fasting blood glucose	

The investigator should make an assessment of the available results with regard to clinically relevant abnormalities. The laboratory results should be signed and dated and retained at the center as source data for laboratory variables. For information on how AEs based on laboratory tests should be recorded and reported, see Section 6.3.

Note: If CK is  $\geq 5$  x ULN, see Appendix D.

Note: If a subject has ALT or AST  $>3$  x ULN, it is recommended to discontinue the investigational product. See Appendix C for further instruction on cases of increases in liver biochemistry values and evaluation of Hy's Law.

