#### **6.3.6 Adverse events based on examinations and tests**

The results from protocol-mandated laboratory tests and vital signs will be summarized in the clinical study report. Deterioration as compared to baseline in protocol-mandated laboratory values, vital signs, and ECGs should therefore only be reported as AEs if they fulfill any of the SAE criteria or are the reason for discontinuation of treatment with the investigational product.

If deterioration in a laboratory value/vital sign/ECG is associated with clinical signs and symptoms, the sign or symptom will be reported as an AE and the associated laboratory result/vital sign will be considered as additional information. Wherever possible, the reporting investigator uses the clinical, rather than the laboratory term (eg, anemia versus low hemoglobin value). In the absence of clinical signs or symptoms, clinically relevant deteriorations in non-mandated parameters should be reported as AE(s).

Any new or aggravated clinically relevant abnormal medical finding at a physical examination as compared with the baseline assessment will be reported as an AE.

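### SAP 4.5.2 counts marked single-enzyme liver elevations by arm for ALT only, so no by-arm count separates an isolated AST rise of at least 3 x ULN with drug continued from a minor rise

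*SAP*

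**What the plan says.** **SAP.** Section 4.5.2 summarises threshold elevations of three analytes. The liver entry reads "Elevations of ALT [≥ 3 times the ULN on single occasions and two consecutive occasions". CK (at least 5 and at least 10 times ULN) and percentage rises in creatinine follow, and all of these "at any time point during the treatment phase will be highlighted and summarised by treatment group at time of occurrence". The same section then has a combined criterion: either transaminase at 3 x ULN or more together with total bilirubin at 2 x ULN or more. The adverse-event listing in SAP 4.4.7 uses the same combination. Hematology and chemistry also go into shift tables by normal-range category (4.5.2). Under 4.5.1, hematology, hepatic biochemistry and "clinical chemistry values outside the laboratory reference ranges will be flagged and summarised", and descriptive statistics are given by visit.

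**Protocol.** Section 3.9 lists "ALT or AST >3 x ULN; see Appendix C for further instruction" among the situations in which the investigator may stop study drug. The note under Table 2 says of the same criterion that "it is recommended to discontinue the investigational product". Appendix C (12.3.3) requires a comprehensive laboratory review for "any patient who meets any of the following identification criteria in isolation or in combination", and lists ALT at 3 x ULN, AST at 3 x ULN and total bilirubin at 2 x ULN (each at or above). Section 6.3.6 says that deteriorations in protocol-mandated laboratory values "should therefore only be reported as AEs if they fulfill any of the SAE criteria or are the reason for discontinuation" of treatment.

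**The concern.** The protocol gives AST the same standing as ALT wherever it sets a single-enzyme liver criterion. The SAP carries only ALT into the by-arm table of marked elevations and gives no reason for leaving AST out.

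This matters because of how Section 6.3.6 divides the work. It keeps most laboratory changes out of adverse-event reporting on the ground that the laboratory results will be summarised in the study report. For a non-serious rise that does not stop treatment, the laboratory tables are therefore the only planned place for a between-arm comparison of the enzyme value. Safety is assessed descriptively, with no formal tests (Protocol 8.5.3), so the choice of table rows decides which comparisons a reader can make. With no AST row, the two arms cannot be compared on isolated AST rises at the level the protocol itself treats as notable.

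**Working it through.** No sample size, power or alpha enters this point, and the plan states no figure to reproduce. The check is a comparison of text, followed by tracing one subject through every planned output that could contain AST.

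**Step 1. Criteria side by side.**

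| Source | Enzymes | Cut-off | Bilirubin also required? |
|---|---|---|---|
| Protocol 3.9 (drug may be stopped) | ALT or AST | above 3 x ULN | no |
| Protocol Table 2 note (stopping recommended) | ALT or AST | above 3 x ULN | no |
| Protocol 12.3.3 (identification) | ALT, AST, each alone | 3 x ULN or more | no (bilirubin at 2 x ULN or more is its own criterion) |
| SAP 4.5.2, threshold summary | ALT | 3 x ULN or more | no |
| SAP 4.5.2, combined criterion | ALT or AST | 3 x ULN or more | yes |
| SAP 4.4.7, listing | ALT or AST | 3 x ULN or more | yes |

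The difference between above 3 and at least 3 does not alter the result.

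**Step 2. The subject traced.** AST at or above 3 x ULN, ALT below 3 x ULN, bilirubin below 2 x ULN, no seriousness criterion met, drug continued.

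| Planned output | What happens to the AST rise |
|---|---|
| ALT threshold summary (SAP 4.5.2) | not counted |
| Combined transaminase and bilirubin summary (4.5.2) | not counted |
| Liver criterion of the listing (4.4.7) | not triggered |
| Shift table (4.5.2) | counted as high, by arm |
| Out-of-range summary (4.5.1) | counted as out of range |
| By-visit statistics (4.5.1) | may show as an arm maximum; no count of subjects |
| Serious adverse event tables (4.4.4) | not included, because not serious |
| Discontinuation adverse events (4.4.6) | not included, because drug continued |

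In the shift table and out-of-range summary, values of 1.1 and 5 times ULN (chosen only to illustrate) fall in the same category.

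**Step 3. Change one condition at a time.**
- Bilirubin at 2 x ULN or more: counted in the combined summary.
- Drug stopped because of the rise: an adverse event under 6.3.6, and in the by-arm discontinuation table.
- Seriousness criterion met: in the serious adverse event tables.
- Symptoms present: under 6.3.6 the symptom is reported as the event and the laboratory value is supporting information.

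The gap is therefore the subject in Step 2 and no wider.

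**Step 4. Are the data there?** Yes. Protocol 5.2.1 puts AST and bilirubin in the abbreviated panel (Visits 8, 10 and 12), and Table 2 includes both in the full panel (Visits 1, 4, 5, 6 and 13).

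**Step 5. Scale.** The documents give no rate of isolated AST elevation, so no expected count can be derived. As a unit only: 543 randomised at 1:1 is 543 / 2 = 271.5 per arm, so one such subject is 1 / 271.5, or about 0.4% of an arm.

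**The case against.** The best case for the SAP has four parts.

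**It does not breach the protocol.** Protocol 8.5.3 promises descriptive summaries of laboratory changes, not a table at every enzyme threshold. The single-analyte criteria in Appendix C are triggers for finding cases. The event that the protocol defines is the combination with bilirubin, and the SAP summarises that for either enzyme. This stands: the point is about completeness and is not a departure from the protocol.

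**AST is not missing from the outputs.** A reader might infer from the ALT-only row that these subjects appear in no between-arm count. The documents do not support that, because the shift table and the out-of-range summary both count them. What is missing is any count at 3 x ULN.

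**Many cases are captured elsewhere.** A reader might also infer that any AST rise meeting the stopping criterion is lost. That is too broad. Where drug is stopped for the rise, as the Table 2 note recommends, the rise reaches the adverse-event tables, as serious rises also do. The gap remains only because Section 3.9 leaves stopping to the investigator, so a subject above the criterion can stay on drug.

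**Some AST rises come from muscle.** This is true, and it bears on how an AST row is read. The CK rows in the same summary give the context.

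The objections narrow the point. They do not supply a by-arm count of isolated AST at 3 x ULN or more.

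**Conclusion.** The point holds in limited form. SAP 4.5.2 isolates marked single-enzyme elevation for ALT only, while the protocol's criteria are ALT or AST. A subject with an isolated, non-serious AST rise to 3 x ULN or more who continues drug is counted by arm only as high or out of range, with no separation from a minor rise.

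The size is unknown and may be zero. Any percentage of under-counting would be invented, because the documents give neither the rate of isolated AST rises nor the number of ALT cases. The conclusion rests on the text of the two documents and on the premise that some subjects above the criterion may stay on drug.

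A reader might extend the argument equally to isolated bilirubin at 2 x ULN or more. The support there is weaker: bilirubin is an identification criterion in Appendix C, but it is not a stopping criterion in Section 3.9 or in the Table 2 note.

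No efficacy estimate, test or analysis population is affected. This is an inexpensive improvement to a descriptive safety table.

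**What to change.** In SAP 4.5.2, extend the liver entry of the threshold summary so that it shows, by treatment group, the number and percentage of subjects with:
- ALT at 3 x ULN or more;
- AST at 3 x ULN or more;
- either enzyme at 3 x ULN or more.

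Give each for single and for two consecutive occasions, using the rule for consecutive occasions that the SAP applies to ALT. Optionally add total bilirubin at 2 x ULN or more, so that the table covers all three Appendix C identification criteria.

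The cost is one amended sentence and a few rows in an existing table, with no new data. The reported count of transaminase elevations may rise slightly, and some added AST rises will be of muscle origin, so the rows should be read alongside CK. The change concerns reporting only and alters no stopping criterion or other clinical rule.
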